Statistical Methods: A 3+3 dose escalation design will be used. The maximum tolerated dose will be exceeded if 2 or more patients out of 6 (or a third or more) experience a dose limiting toxicity (DLT) at that dose. The dose immediately below will be recommended for further study. DLTs are defined as any acute toxicity of Grade 4 nausea, Grade 4 skin toxicity, Grade 3+ liver toxicity (metabolic or ascites), or Grade 3+ enteritis. Severe late toxicities of interest (occurring beyond the 4 week period of evaluation and up to 12 months after RT) will include any Grade 3+ gastrointestinal toxicity (such as small bowel ulcer, stricture, perforation, bleed, liver damage, pancreatitis, or cholecystitis). If the rate of any severe late toxicity of interest exceeds 25% (i.e., 7 or more patients in the expanded cohort of 18 treated at the MTD), the study committee will suspend accrual and determine whether further dose modifications are needed; the protocol will be amended accordingly.

TABLE OF CONTENTS

SCHEMA	ii
1. OBJECTIVES	1
1.1. Primary Objectives	1
1.2. Secondary Objectives	1
2. BACKGROUND	1
2.1 Unresectable carcinoma of the pancreas	1
2.2 Rationale	1
3. PATIENT SELECTION	3
3.1 Eligibility Criteria	3
3.2 Exclusion Criteria	3
3.3 Inclusion of Women and Minorities	4
4. TREATMENT PLAN	4
4.1 Radiation Therapy dose escalation	4
4.2 Measuring Health Related Quality of Life	4
4.3 Definition of Dose-Limiting Toxicity	5
4.4 General Concomitant Medication and Supportive Care Guidelines	7
4.5 Duration of Therapy	7
4.6 Duration of Follow Up	8
4.7 Criteria for Removal from Study	8
5. RADIATION THERAPY GUIDELINES	8
5.1 Treatment related planning procedures	8
5.2 RT planning parameters	8
5.3 RT Treatment	10
6. ADVERSE EVENTS	10
7. STUDY CALENDAR	133
8. MEASUREMENT OF EFFECT	144
8.1 Antitumor Effect – Solid Tumors	144
9. STATISTICAL CONSIDERATIONS	155
9.1 Study Design/Endpoints	155
9.2 Sample Size/Accrual Rate	166
9.3 Analysis of Secondary Endpoints	166
10. CONFIDENTIALITY	166
10.1 Patient confidentiality issue	17
REFERENCES	18
APPENDIX A	20
APPENDIX B	21
APPENDIX C	22
APPENDIX D	23

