4.3 Definition of Dose-Limiting Toxicity

The evaluation period of acute toxicity will be defined by the period of 28 days following the first fraction of RT. Dose Limiting Toxicity (DLT) will be defined according to Common Toxicity Criteria version 3.0 (See Appendix B) and includes the following acute toxicities:

- Grade 4 nausea (life-threatening consequences)
- Grade 4 skin toxicity (necrosis or ulceration of full thickness dermis, spontaneous bleeding from involved site)
- Grade 3+ liver toxicity including symptomatic ascites requiring invasive procedure, or total bilirubin $>3 \times$ ULN, or AST $>5 \times$ ULN, or ALT $>5 \times$ ULN that persists until day 28, and is attributable to radiation therapy.
- Grade 3+ enteritis (abdominal pain, fever, change in bowel habits with ileus, peritoneal signs) that is attributable to radiation therapy.

Patients must have a minimum of 3 weeks of follow-up after RT start for patient data to contribute enough follow-up for consideration of dose-limiting toxicity. However, any DLT that occurs with shorter follow-up will count towards the dose escalation rules. In addition, any grade 5 toxicity (i.e., death) considered possibly, probably or likely related to RT will be considered a DLT.

Any late toxicity that occurs beyond the 4 week period of evaluation will be closely followed and documented as a toxicity of interest. Included are the following severe late toxicities of RT:

- Grade 3+ gastrointestinal ulcer, fistula, stricture, or perforation (symptomatic and severely altered GI function, IV fluids or TPN ≥ 24 hrs, intervention indicated)
- Grade 3+ gastrointestinal mucositis (confluent ulcerations or pseudomembranes, bleeding with minor trauma)
- Grade 3+ gastrointestinal bleed (transfusion, interventional radiology or endoscopic or operative intervention)
- Grade 3+ gastrointestinal necrosis (inability to aliment adequately by GI tract, interventional radiology, intervention indicated)
- Grade 3+ liver toxicity including symptomatic ascites requiring invasive procedure, or total bilirubin $>3 \times$ ULN, or AST $>5 \times$ ULN, or ALT $>5 \times$ ULN, or asterixis, that is attributable to radiation therapy.

- Grade 3+ enteritis (abdominal pain, fever, change in bowel habits with ileus, peritoneal signs) that is attributable to radiation therapy.
- Grade 3+ pancreatitis (interventional radiology or operative intervention indicated)

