- Grade 3+ cholecystitis (interventional radiology or operative intervention indicated)

These severe, late toxicities will be evaluated between 1 and 12 months of therapy. There is no minimum follow-up time after RT start required for patient data to contribute enough follow-up for toxicities of interest.

Enrollment of 12 additional toxicity-evaluable patients at the MTD will provide a cohort of 18 patients at the putative MTD. If six or fewer of the 18 patients experience a toxicity of interest during the evaluation period, the combination will be considered tolerable. If 7 or more patients experience a toxicity of interest, the study committee will suspend accrual and determine whether further dose modifications are needed; the protocol will be amended accordingly. If the true probability of DLT at the MTD is 50%, the combination will be identified as too toxic with probability 0.88. If the true probability of DLT at the MTD is 25%, the combination will be identified as having an acceptable toxicity profile with probability 0.86.

Management associated with the above adverse events is outlined in Section 7.

Dose escalation will proceed within each cohort according to the following scheme. Dose-limiting toxicity (DLT) is defined above.

Number of Patients with DLT at a Given Dose Level	Escalation Decision Rule
0 out of 3	Enter 3 patients at the next dose level
≥ 2	Dose escalation will be stopped. This dose level will be declared the maximally administered dose (highest dose administered). Three (3) additional patients will be entered at the next lowest dose level if only 3 patients were treated previously at that dose.
1 out of 3	Enter at least 3 more patients at this dose level. 
 • If 0 of these 3 patients experience DLT, proceed to the next dose level. • If 1 or more of this group suffer DLT, then dose escalation is stopped, and this dose is declared the maximally administered dose. Three (3) additional patients will be entered at the next lowest dose level if only 3 patients were treated previously at that dose.
≤ 1 out of 6 at highest dose level below the maximally administered dose	This is generally the recommended phase 2 dose. At least 6 patients must be entered at the recommended phase 2 dose.

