6. ADVERSE EVENTS

Adverse event (AE) monitoring and reporting will be performed.

- Radiation side effects are limited to the area involved in the treatment field. Acute and late toxicity related to radiation therapy may include fatigue, nausea and vomiting, skin erythema, subcutaneous fibrosis, esophagitis, pericarditis, diarrhea, myelitis, damage to the small bowel (including stricture or obstruction, bleed, fistula formation, or perforation), liver dysfunction, kidney damage, and radiation enteritis.
- Acute toxicity including Grade 4 nausea, Grade 4 skin toxicity, and Grade 3 liver toxicity will be referred to as dose limiting toxicities (DLT).
- Late toxicity including any Grade 3+ GI toxicity (small bowel damage including stricture or obstruction, bleed, fistula formation, or perforation; liver damage including ascites but not including abnormal lab values only; pancreatitis, cholecystitis) will be considered a toxicity of interest.
- All life-threatening Grade 4 and all fatal toxicities (Grade 5) must be reported immediately and evaluated.

- Acute toxicity: Acute side effects are considered as occurring \leq 28 days from the start of radiation therapy. They will be documented using the NCI Common Terminology Criteria for Adverse Events (CTCAE) version 3.0 (A copy can be downloaded from <http://ctep.info.nih.gov>). The relevant sections are included in the appendix.
- Late toxicity: Late side effects are considered as occurring $>$ 28 days from the start of radiation therapy through a 12 month total evaluation period. They will also be documented using the NCI Common Terminology Criteria for Adverse Events (CTCAE) version 3.0. The relevant sections are included in the appendix.
- University of Chicago Reporting Guidelines
 - If the reaction requires reporting, the Research Nurse or MD reports the adverse reaction to the Cancer Clinical Trials Office (CCTO) at [contact] by the end of the business day when he/she becomes aware of the event. Events occurring after business hours will be reported to the CCTO by 12 pm (noon) the next business day.
 - The following information is required when calling in the event:
 - Caller's Name and Telephone Number
 - Patient Initials
 - Patient Medical Record Number
 - IRB Protocol Number
 - PI of Study
 - Attending Physician
 - Date of Event
 - Description of Event (including grade of the event and attribution of the event and if the event required hospitalization)

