7. STUDY CALENDAR

Baseline evaluations (including pain score, performance status, and medications) are to be conducted within 21 days prior to start of protocol therapy. Scans must be done within 28 days prior to the start of therapy. In the event that the patient's condition is deteriorating, laboratory evaluations should be repeated within 48 hours prior to initiation of therapy.

	Pre-treatment	Week 1 of RT	Week 2 of RT	Post-treatment
Inclusion/exclusion	X			
Informed consent	X			
Pathology confirming cancer	X			
History and physical	X	X	X	X ^f
Vital signs	X	X	X	X ^f
Performance status and pain score	X	X	X	X ^f
Documentation of current medicines	X	X	X	X ^f
CT or MRI of abdomen ^a	X			X ^a
Hematology ^b	X	X	X	X ^f
Chemistry ^c	X	X	X	X ^f
β-HCG ^d	X			
Patient QOL Questionnaire	X			X ^f
Toxicity assessment ^e		X ^e	X ^e	X ^f

a = Imaging will be done within 28 days of RT start, and in follow up at 3-5 weeks after completion of RT.

Further abdominal imaging will be performed every 6 months for the first year after RT.

b = CBC with differential, platelet count

c = comprehensive metabolic profile (glucose, sodium, potassium, chloride, carbon dioxide, BUN, creatinine, calcium, total bilirubin, alkaline phosphatase, AST, ALT). CA19-9 will be measured at months 1, 6, 12 from the start of radiation therapy, then every 6 months indefinitely (off protocol).

d = for women of child bearing potential, serum beta-hCG

e = prior to each radiation treatment after the first fraction, and with all other post-treatment clinic visits

f = From the start of radiation therapy, visits will be q2 weeks for the first month; then at months 2, 4, 6, 9, and 12; then every 6 months indefinitely (off protocol).

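### Section 4.3 counts a liver laboratory DLT only if it lasts to study day 28, a condition that the schema and Section 6 lack and that cannot be judged at the 3-week evaluability point

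*Combined protocol and SAP*

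**What the plan says.** Section 4.3 sets the window: "The evaluation period of acute toxicity will be defined by the period of 28 days following the first fraction of RT". Within it, the liver DLT is a Grade 3 or higher toxicity. The item lists ascites needing an invasive procedure, bilirubin above 3 times the upper limit of normal (ULN), AST above 5 times and ALT above 5 times, and closes with "ULN that persists until day 28, and is attributable to radiation therapy". The closing clause directly follows ALT. The text gives no minimum duration and no separate treatment of Grade 4 values. The nausea, skin and enteritis items have no persistence condition.

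The escalation table in the same section relies on this text: "Dose-limiting toxicity (DLT) is defined above".

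Two other places define the liver DLT without persistence. The Statistical Methods paragraph of the schema has "Grade 3+ liver toxicity (metabolic or ascites), or Grade 3+ enteritis". Section 6 lists Grade 3 liver toxicity among the acute DLTs.

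On timing, Section 4.3 says "Patients must have a minimum of 3 weeks of follow-up after RT start" for a patient to be considered for DLT. The study calendar (Section 7, footnote f) says "From the start of radiation therapy, visits will be q2 weeks for the first month", and chemistry follows that schedule after the checks in weeks 1 and 2 of RT. Section 6 starts the late period after day 28 and runs it to 12 months.

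**The concern.** The condition tests whether an abnormality is still present on one study day. Whether a liver event counts then depends on when it starts and ends within the window as well as on its severity. An early event that resolves in time drops out of the acute count and never enters the late count.

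Two people working from different sections of the same protocol could classify one patient differently. In a 3+3 design one patient can change the decision: with 0 of 3 the dose goes up, with 1 of 3 the cohort is expanded, and with 2 or more escalation stops. The DLT count determines the MTD, which is the primary objective.

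The 3-week minimum adds a timing problem. A patient with an elevation still open at day 21 already has enough follow-up to be considered, but cannot yet be classified under a rule that looks at day 28.

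**Working it through.** **Plan's own figures.** The documents give no operating characteristics for the DLT rule. The nearest figures, 0.88 and 0.86 in Section 4.3, belong to the 7-of-18 rule for late toxicities. Both reproduce by exact binomial: P(X ≥ 7 | 18, 0.50) = 0.881 and P(X ≤ 6 | 18, 0.25) = 0.861. This point does not change them.

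**Classifying example patients.** The records are invented, days count from the first fraction, and attribution to RT is assumed throughout. Appendix B puts AST or ALT above 20 × ULN at Grade 4.

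| Record | Section 4.3 | Schema | Late (after day 28) |
|---|---|---|---|
| ALT 25 × ULN, days 5–26 (26 − 5 + 1 = 22 days) | Not a DLT | DLT | No |
| Bilirubin 4 × ULN, days 7–20 | Not a DLT if the clause covers bilirubin; otherwise a DLT | DLT | No |
| ALT 5.2 × ULN, days 14–28 | DLT | DLT | No |
| ALT 5.2 × ULN, first seen on the day-28 sample | Depends on whether persisting requires an earlier onset | DLT | No, unless it continues |

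The first row is firm. Even on the narrowest reading the clause covers ALT, so the 22-day Grade 4 episode is outside the 4.3 count. Section 6 also has no persistence condition. It names Grade 3 where the schema says Grade 3 or higher, so a Grade 4 value is a DLT there only if Grade 3 is read as a minimum.

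**Timing.** Visits every 2 weeks in month 1 put scheduled chemistry at about day 14 and day 28. If ALT first exceeds its limit at the later sample, that single value does not show how long it has been raised. If ALT has been raised since day 5 and is still raised on day 21, the 3-week minimum is met, yet the day-28 condition is unresolved for another 28 − 21 = 7 days.

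**Illustrative size.** Assumptions, none of them in the documents: 10% of patients have some other DLT; independently, a share q have an RT-attributable Grade 3 or higher laboratory episode lasting D = 14 days; onset is uniform over days 1–28.

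- P(episode present on day 28) = D/28 = 14/28 = 0.50.
- DLT rate if every episode counts: p = 1 − 0.90 × (1 − q).
- DLT rate under the day-28 condition: p = 1 − 0.90 × (1 − 0.5q).
- P(clear a level) = (1 − p)³ + 3p(1 − p)⁵, i.e. 0 of 3, or 1 of 3 followed by 0 of 3.

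| q | p, all count | P(clear) | p, day-28 condition | P(clear) |
|---|---|---|---|---|
| 5% | 0.145 | 0.625 + 0.199 = 0.82 | 0.1225 | 0.676 + 0.191 = 0.87 |
| 10% | 0.190 | 0.531 + 0.199 = 0.73 | 0.145 | 0.625 + 0.199 = 0.82 |

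D/28 includes an onset on day 28 itself. If persisting requires an earlier onset, the fraction is 13/28 = 0.464, and the day-28 results become 0.87 (q = 5%) and 0.83 (q = 10%). The disputed reading hardly matters to the size.

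**The case against.** The strongest defence is that counting only abnormalities unresolved at the end of the window is a legitimate choice. Section 3.1.7 admits patients with bilirubin up to 2.5 × ULN, close to the DLT limit of 3 × ULN, and Section 2.1 names biliary obstruction among the local consequences of this disease. A persistence condition may be deliberate. That stands: the documents do not state its purpose, so one cannot assume that it was meant to screen out brief changes, or that a duration counted from onset would be the correct rule.

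It can also be said that severe events do not go unseen. Section 6 requires immediate reporting of life-threatening Grade 4 and fatal toxicities, and toxicities are reviewed at weekly meetings. In addition, 4.3 counts any related death as a DLT. This is correct, but reporting an event does not make it count in the escalation table.

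A reader might infer that a one-day rise on day 28 is definitely a DLT while a three-week rise is not. The documents do not support the first half. A value first seen on day 28 has hardly persisted in the ordinary sense, attribution to RT is also required, and samples two weeks apart could not show that it lasted one day.

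A reader might also infer a very large effect. If all DLTs were 14-day liver laboratory episodes at a 30% rate, P(clear) would go from 0.49 (p = 0.30) to 0.81 (p = 0.15). Nothing in the documents supports that mix. For single-fraction SBRT alone, Section 2.2 cites roughly 10% severe toxicity, and the late events it lists are ulcers, strictures and a perforation. The comparison there, like the one in the working, is with a rule that has no persistence condition at all.

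**Conclusion.** The point holds in a limited form. Under Section 4.3, which governs escalation, an RT-attributable Grade 3 or 4 ALT elevation that resolves before study day 28 enters neither the DLT count nor the late-toxicity count. The schema counts it, and Section 6 sets no persistence condition. The same may apply to AST and bilirubin, depending on how far the clause reaches. The 3-week evaluability minimum conflicts with a criterion fixed at day 28, and one sample near day 28 cannot establish persistence.

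This can misclassify a patient in the 3+3 and so affect the MTD. Relative to counting every episode, the condition favours escalation. Its size is unknown because the documents give no rate for transient liver laboratory events. Under the illustrative assumptions it raises the chance of clearing a level by about 0.04 at a 5% episode rate (0.824 to 0.867) and 0.09 at 10% (0.730 to 0.824), and it vanishes if such episodes do not occur. No sample-size figure or stated probability changes.

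**What to change.** Reconcile the schema, Section 4.3 and Section 6 into one liver DLT definition, and have the escalation table point to it. That definition should state:

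- whether a persistence condition applies at all, and if so to which of bilirubin, AST, ALT and ascites, and to which grades;
- if it is kept, how persistence is established, including what happens when the first elevation appears at the week-4 sample;
- how the 3-week evaluability minimum fits with it, so that no patient with an unresolved elevation is counted as DLT-free before the condition can be assessed.

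Which clinical rule to adopt is for the sponsor and investigators. The cost is a wording change, plus occasionally a repeat chemistry or a few days' wait before a cohort decision.

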5.1 Treatment Related Planning Procedures

- 5.1.1. All patients will be evaluated prior to simulation for placement of fiducial markers (by endoscopic approach or interventional radiology) in or around the primary tumor, for purposes of stereotactic localization prior to SBRT. Marker placement is preferred but not required.
- 5.1.2. When done, the ideal timing of MRI will be ≥ 2 days after placement of fiducial markers.
- 5.1.3. All patients will undergo CT simulation ≥ 2 days after placement of markers, and prior to the first treatment using appropriate immobilization. Patients should have no food 2 hours prior to undergoing simulation. However, medications may be taken with liquid.
- 5.1.4. Patients will be positioned in a stable position capable of allowing accurate reproducibility of the target position from treatment to treatment.
- 5.1.5. Simulation with respiratory gating and acquisition of a 4D CT scan for retrospective respiration phase-based imaged sorting is highly preferred but not required.

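### Section 4.3 accepts 3 weeks of follow-up for a DLT-free patient although its own DLT window is 28 days, and nothing requires day 28 before escalation

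*Combined protocol and SAP*

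**What the plan says.** Section 4.3 fixes the window: "The evaluation period of acute toxicity will be defined by the period of 28 days following the first fraction of RT". Section 6 uses the same limit for acute effects ("28 days from the start of radiation therapy. They will be documented using the NCI" Common Terminology Criteria). Within the liver DLT definition, at least one laboratory criterion counts only if it is one "that persists until day 28, and is attributable to radiation therapy".

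On who counts, Section 4.3 states: "Patients must have a minimum of 3 weeks of follow-up after RT start for patient data to contribute enough follow-up" for DLT consideration. It then adds: "However, any DLT that occurs with shorter follow-up will count towards the dose escalation rules".

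The escalation table in Section 4.3 works on counts alone. For 0 of 3 the instruction is "Enter 3 patients at the next dose level", with no timing condition. For the final dose it adds: "At least 6 patients must be entered at the recommended phase 2 dose".

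The other relevant places set no waiting rule either:
- Section 6 provides for weekly safety review.
- Section 7, footnote f, schedules visits every 2 weeks in the first month.
- Section 8.1.1 makes every patient evaluable for toxicity from the first treatment.
- Section 9.1 restates the 2-of-6 criterion.

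**The concern.** The window and the minimum follow-up do not match. At day 21 a patient has been observed for 21/28 = 75% of the window. A patient with raised liver values cannot yet be classified on the persistence criterion. The sentence about shorter follow-up covers DLTs already seen. It does not say what to do with a DLT-free patient at days 21 to 27, or with a DLT that appears after the next level has opened.

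The MTD is the primary objective, and each decision turns on 0, 1 or 2 events in 3 to 6 patients. Counting a patient as DLT-free too soon can only lower the count. One unseen DLT turns 1 of 3 into 0 of 3 and opens the next dose level to new patients.

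**Working it through.** **The plan's own figures.** Section 4.3 gives operating characteristics only for the 18-patient cohort. They reproduce: P(X ≥ 7 | n = 18, p = 0.50) = 0.881 (stated 0.88), and P(X ≤ 6 | n = 18, p = 0.25) = 0.861 (stated 0.86). They do not depend on the 3-week rule. The plan gives no figure for the 3+3 stage.

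**Inputs from the plan.** Window 28 days (4.3, 6); minimum 21 days (4.3); escalate on 0 of 3, or on 1 of 3 followed by 0 of 3 (4.3); accrual 1–2 patients per month (9.2).

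**Assumptions.** True DLT rate p of 1/3 or 0.40. Share L of DLTs that first appear after day 21: 0.25 under uniform onset, range 0.10 to 0.50. The persistence criterion is left out and could add to the effect.

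**Step 1: everyone followed to day 28.** P(escalate) = (1−p)³ + 3p(1−p)⁵.
- p = 1/3: 0.296 + 0.132 = 0.428.
- p = 0.40: 0.216 + 0.093 = 0.309.

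**Step 2: decision when the last patient of a trio reaches day 21.** With even accrual at 2 per month, patients are 30.4/2 = 15.2 days apart. The second patient is then at day 36, so only the third is cut short. Let q = p(1−L), and let the first trio be complete by the second decision:
- P0 = (1−p)²(1−q)
- P1 = 2p(1−p)² + (1−p)²q
- P(escalate) = P0(1 + P1)

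For p = 1/3 and L = 0.25: q = 0.25, P0 = 0.333, P1 = 0.407, giving 0.333 × 1.407 = 0.469.

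| Share of DLTs after day 21 | p = 1/3 | p = 0.40 |
|---|---|---|
| 0 (full window) | 0.428 | 0.309 |
| 0.10 | 0.445 | 0.327 |
| 0.25 (uniform) | 0.469 | 0.352 |
| 0.50 | 0.508 | 0.392 |

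**Step 3: accrual and start-up lag, uniform onset.** If the decision waits for the next patient at even spacing s = 30.4/rate days, L = max(0, (28 − max(21, s))/28). A lag of d days from dose assignment to first fraction gives L = (7 − d)/28. Some lag is plausible, since after marker placement CT simulation must be at least "2 days after placement of markers, and prior to the first treatment using appropriate immobilization", but the plan gives no total. Random (Poisson) arrivals were simulated.

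| Scenario | p = 1/3 | p = 0.40 |
|---|---|---|
| Even, 1 per month (s = 30.4), wait for next patient | 0.428 | 0.309 |
| Even, 1.25 per month (L = 0.13), wait for next patient | 0.450 | 0.332 |
| Even, about 1.45–2 per month (L = 0.25) | 0.469 | 0.352 |
| Poisson, 1–2 per month, decide at day 21 | 0.474–0.479 | 0.357–0.363 |
| Poisson, 1–2 per month, wait for next patient | 0.454–0.469 | 0.336–0.352 |
| Lag 3 days (L = 0.14) | 0.452 | 0.334 |
| Lag 7 days (L = 0) | 0.428 | 0.309 |

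**Step 4: the sentence read as a floor for dropouts.** Suppose one first-trio patient is lost at day 21 and all others are complete. Then P0 + [2p(1−p)(1−q) + (1−p)²q](1−p)³ = 0.465 (p = 1/3) and 0.348 (p = 0.40).

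**Step 5: final recommended dose.** Let E1 and E2 be the step-2 probabilities at levels 1 and 2, and let B(p) = P(Bin(6, p) ≤ 1) on complete data:
- rec3 = E1·E2·B3
- rec2 = E1·B2·(1−B3)
- rec1 = B1·[1 − E2·B3 − B2·(1−B3)]

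The table shows the chance of recommending a level with a true rate of at least one third:

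| Assumed DLT rates, levels 1/2/3 | L = 0 | L = 0.25 | L = 0.50 |
|---|---|---|---|
| 10/20/33% | 0.225 | 0.237 | 0.247 |
| 20/33/50% | 0.255 | 0.268 | 0.280 |
| 33/45/60% | 0.364 | 0.371 | 0.378 |

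**The case against.** The strongest reply is that the 3-week sentence defines who is in the denominator, not when to decide. Section 4.3 uses nearly the same wording for late toxicity, where it sets no minimum follow-up. That cannot mean the tolerability decision is taken at time zero. On this reading the 0.465 of step 4 applies only when a patient is actually lost. With an assumed 2%, 5% or 10% chance of loss at day 21 per patient, the rise at p = 1/3 is 0.3, 0.8 or 1.6 points. The first scheduled visit that satisfies 3 weeks also falls at about day 28, and weekly review may catch later events.

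This reading is plausible, and it makes the effect small. It does not remove the mismatch: a patient lost on days 21 to 27 still counts as DLT-free. No section makes the week-4 visit a condition of escalation, and weekly review may pick up an event only after the decision.

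Two further points stand in part. The final-dose formula does not return to a level whose completed data later show 2 or more DLTs, so its 1 point leans high. Replacements also press on the cap of 24, since 3 + 3 + 18 = 24 uses all of it. However, the plan's own path with both lower levels expanded, 6 + 6 + 18 = 30, already exceeds that cap.

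**Conclusion.** The concern holds. Section 4.3 states a minimum follow-up that is shorter than its own DLT window and incompatible with a criterion that needs day 28, and no other section closes the gap. The text permits early counting; it does not require it.

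Under uniform onset the chance of escalating past a level with a true DLT rate of one third or 40% rises by 0 to about 5 points per decision. If half of DLTs came after day 21, the rise would be about 8 points (0.428 to 0.508, and 0.309 to 0.392). The final recommended dose moves by about 1 point under uniform onset, because at least 6 patients must be treated there and later DLTs still count. All sizes rest on assumed DLT timing, accrual pattern and dose–toxicity curves. The effect is zero if every patient is followed to day 28 before each decision. This should be fixed because it governs the primary endpoint and the error runs only towards escalation, although the numerical effect is modest.

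**What to change.** In Section 4.3, replace the 3-week minimum with follow-up through day 28 from the first fraction for any patient counted as DLT-free in an escalation decision. Replace a DLT-free patient who leaves before then. Keep the rule that a DLT seen earlier counts. State which liver criteria the persistence clause covers.

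Section 3.2.2 counts the DLT observation period as 28 days post-RT, whereas Sections 4.3 and 6 count from the start of RT. These must be reconciled by the clinical team; if the anchor changes, the minimum follow-up should change with it. As separate housekeeping, the DLT list in Section 6 omits enteritis, and its acute and late lists should be reconciled with Section 4.3.

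The cost is a wording amendment, up to about one week's delay per escalation decision, and an occasional replacement patient. The sample-size statement in Section 9.2 should allow for replacements. No visit is added: the calendar already has a week-4 visit with toxicity assessment and chemistry.

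### A non-fatal Grade 3+ GI injury on days 1-28 that is not coded as enteritis or liver toxicity counts toward neither the 3+3 nor the 7-of-18 rule

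*Combined protocol and SAP*

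**What the plan says.** **Days 1-28.** Section 4.3 sets the acute window: "The evaluation period of acute toxicity will be defined by the period of 28 days following the first fraction of RT". It then introduces the dose-limiting toxicities: "Dose Limiting Toxicity (DLT) will be defined according to Common Toxicity Criteria version 3.0 (See Appendix B) and includes the following acute toxicities". Four items follow: Grade 4 nausea, Grade 4 skin toxicity, Grade 3+ liver toxicity and Grade 3+ enteritis. The same section makes any RT-related Grade 5 toxicity a DLT. The Schema (Statistical Methods) words the four items as a definition: "any acute toxicity of Grade 4 nausea, Grade 4 skin toxicity, Grade 3+ liver toxicity (metabolic or ascites), or Grade 3+ enteritis". Section 6 gives a shorter list without enteritis: "Acute toxicity including Grade 4 nausea, Grade 4 skin toxicity, and Grade 3 liver toxicity will be referred to as dose limiting toxicities (DLT".

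**After day 28.** Section 4.3 says: "Any late toxicity that occurs beyond the 4 week period of evaluation will be closely followed and documented as a toxicity of interest". Its late list holds Grade 3+ ulcer, fistula, stricture, perforation, mucositis, bleed, necrosis, liver toxicity, enteritis, pancreatitis and cholecystitis. It adds: "These severe, late toxicities will be evaluated between 1 and 12 months of therapy". Section 6 agrees on the boundary: "Late side effects are considered as occurring" more than 28 days from the start of RT, through month 12.

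**Rules.** The escalation table in Section 4.3 counts DLTs only. The tolerability rule counts patients with a toxicity of interest among the 18 at the putative MTD. Six or fewer is tolerable, and seven or more suspends accrual.

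**The concern.** The windows meet at day 28, but the lists do not match. Nine kinds of GI injury that the plan treats as severe after day 28 have no line of their own in the acute list. Section 6 names bowel stricture, bleed, fistula and perforation among effects that may be acute or late, so the plan itself allows for them early.

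The primary objective is the MTD and the appropriate dose. Section 2.2 gives the need to characterise GI toxicity better as a reason for the trial. Under the rules as written, a dose level could be cleared, and the dose then called tolerable, with such events left out of both counts. Whether an event counts would depend on its start date, or on whether the site codes it as enteritis.

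**Working it through.** **1. Follow single events through both rules.** The grades are those of Appendix B.

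| Event | By day 28: 3+3 | By day 28: 7-of-18 | Starting after day 28: 7-of-18 |
|---|---|---|---|
| Grade 3 GI bleed (transfused, not life-threatening), resolved by day 28 if early | no | no | yes |
| Grade 3 pancreatitis or cholecystitis, resolved by day 28 if early | no | no | yes |
| Ulcer, fistula or stricture, Grade 3+, starting by day 28 and persisting | no, unless coded as enteritis | not stated | yes |
| Life-threatening bowel bleed or perforation, coded as RT-attributable Grade 4 enteritis | yes (Section 4.3, Schema) | no | yes |

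The first row does not reach the DLT list through enteritis. Appendix B puts blood in the stool at Grade 2 enteritis. Grade 3 is described by pain, fever, ileus and peritoneal signs, and Grade 4 by life-threatening consequences. The acute table has no row for hemorrhage, ulcer, perforation, fistula, stricture, mucositis, necrosis, pancreatitis or cholecystitis. Those rows are in the late table only.

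**2. Reproduce the plan's figures.** Section 4.3 states 0.88 (too toxic at 50%) and 0.86 (acceptable at 25%). With X binomial and n = 18:
- P(X ≥ 7 | p = 0.50) = 0.881
- P(X ≤ 6 | p = 0.25) = 0.861

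Both agree, so there is no arithmetic error.

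**3. Illustrate the 7-of-18 rule.** Let f be the share of affected patients whose only qualifying event falls by day 28 and is uncounted. The documents give no value for f, so the values here are assumptions. The counted rate is 0.50 × (1 − f).
- f = 0: rate 0.50, P(X ≥ 7) = 0.881
- f = 0.10: rate 0.45, P(X ≥ 7) = 0.774
- f = 0.20: rate 0.40, P(X ≥ 7) = 0.626
- f = 0.30: rate 0.35, P(X ≥ 7) = 0.451

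**4. Illustrate one 3+3 step.** With per-patient DLT probability p, the chance of escalating is E(p) = (1 − p)³ + 3p(1 − p)⁵. Assume a listed-DLT probability of 10%.
- As written: E(0.10) = 0.729 + 0.177 = 0.906, whatever the rate of unlisted early events.
- If a further 5% of patients had an early unlisted event and it counted: E(0.15) = 0.814.
- If a further 10% did: E(0.20) = 0.709.

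These added rates are also assumptions.

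**The case against.** A reader might infer that every early Grade 3+ GI event escapes every decision. The documents do not support that. An RT-related death is a DLT whatever its type. Enteritis is the only bowel-injury row in the acute table, and its Grade 4 description names perforation, bleeding, ischemia and necrosis. Coding a life-threatening early bowel bleed or perforation there follows the plan's own scheme and makes it a DLT if attributed to RT. This stands, and the point is limited accordingly. Section 6 weakens the route somewhat by leaving enteritis off its DLT list.

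The lead-in to the list in Section 4.3 can be read as open-ended, as can Section 6. The Schema's wording is that of a closed definition, and no text says which further events would qualify, so this reading does not close the gap.

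A reader might also infer that such early events are expected to be common. Section 2.2 does not say so. It reports ulcer, stricture and perforation as late toxicity on longer follow-up of the single-fraction series, and no Grade 3+ toxicity in that series' initial report. It puts severe toxicity at about 10% with SBRT alone. At a true rate of 10% the 7-of-18 rule flags with probability of about 0.001 even if every event counts, so the gap would hardly change that rule's result.

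Nor would these events go unseen. Toxicity is assessed from week 1 and reviewed weekly, and Grade 4 and 5 events are reported immediately. That stands, but none of it is tied to the escalation or tolerability rule.

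**Conclusion.** The gap is real but narrower than it may first appear. It covers non-fatal Grade 3+ GI ulcer, bleed, perforation, fistula, stricture, mucositis, necrosis, pancreatitis or cholecystitis on days 1-28, when not coded as enteritis or liver toxicity. Neither formal rule counts these. It is certain for events that resolve by day 28. For events that persist, the text does not say how they are scored.

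This follows from the wording and needs no numerical assumption. Its size cannot be derived from the documents. The fall from 0.88 to between 0.77 and 0.45 rests on the plan's own 50% scenario, an assumed early share of 10% to 30%, and no later qualifying event in the same patient. The stated operating characteristics are correct for the events that the rule counts.

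**What to change.** Reconcile the Schema, Section 4.3, Section 6 and Appendix B on three points:
- Every Grade 3+ GI event on the late list should count under at least one of the two rules whenever it occurs from the first fraction to month 12.
- The scoring of an event that starts by day 28 and continues beyond it should be stated.
- The DLT list should be the same in all places, including whether enteritis is on it.

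Simply opening the whole toxicity-of-interest window at the first fraction is not enough. It would leave the 3+3 unchanged. It would also bring the late liver criterion into days 1-28 without the acute rule's requirement that the abnormality persist until day 28. That acute liver criterion should stay as it is for days 1-28. Which early events are dose-limiting is for the sponsor and investigators to decide.

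The cost is a wording amendment, since toxicity is already assessed from week 1. The toxicity count can only rise, so the dose is slightly less likely to be called tolerable. For scale, suppose the added events go to the 7-of-18 rule, the true rate is 25% and the assumed early share is 20%. The chance of suspension then rises from 0.051 (counted rate 0.25 × 0.80 = 0.20) to 0.139. The latter is the false-alarm rate that the plan already accepts (1 − 0.861).
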